14.4 Data Review

The study coordinator will review all REDCap forms for accuracy and completion prior to submitting them to the REDCap database. If issues are identified post-submission, the study coordinator will contact the appropriate person at the Coordinating Center to address the issue. Only the Coordinating Center is authorized to add missing data or make any changes to submitted data in REDCap. The Coordinating Center may conduct further investigations if certain fields are associated with a higher rate of form errors.

14.5 Data Entry

Once the study coordinator has reviewed the completed REDCap forms, they will submit the electronic forms to the REDCap database. The data manager at the Coordinating Center will review the data for accuracy and completion.

14.6 Data Transfer

The Coordinating Center will access the data through a secure, online REDCap database system. The database manager will download the data sets and conduct checks for completeness and validity. Any queries generated will be communicated by secure encrypted email to the study coordinator for resolution.

14.7 Data Entry Errors

The data manager at the CC will assess study data using an automated program in REDCap (with a goal of completing within 2 days of data entry), searching for missing and contradicting data fields. Wherever there is a mismatch, an error file is generated with relevant data such as the form, field name, and data for which discrepancy is found. The data manager will then contact the study coordinator to verify the forms. Discrepancies and missing values will be assessed by the data manager, and resolved by queries sent to the study coordinator and appropriate observers (e.g., clinician). A logfile will preserve the date and time of any changes, together with who entered the changes.

14.8 Data Consistency and Validity

Through range checks, the data entry software helps prevent inconsistencies or invalid data. The database program will check for the following errors: (1) improper entry of the patient ID based on the checksum, (2) data fields that are out of range, (3) inconsistent or illogical entries, (4) incompleteness, and (5) numerical values that are far outside the range of those previously entered. The software will create an error file with relevant data such as the form identification, field names and the data. Automated checks will be made to ensure consistency and that each variable in the analysis set has in-range values (protecting against negative ages, spelling errors in categorical factors, and similar errors). The data manager will contact the study coordinator about any errors in order to resolve the inconsistencies.

14.9 Data Preparation and Cleaning

Datasets for analysis will be produced in comma separated values (.csv) files containing a single header line whose variable names match the REDCap database. Each analysis set will be in the form of a rectangular table in which each column corresponds to a single variable and each row to an observation. All missing values will be coded explicitly using the string "NA" (as used in the R software). Codes for categorical variables (such as 1 for male, and 2 for female) will be avoided in favor of self-documenting character strings or factor variables (such as Male, Female).

A detailed codebook will be prepared, containing for each variable, (a) the form from which the variable derived, (b) the text of the question, (c) all possible values for the variable, and (d) summary statistics for the variable. Note that all codes and character strings that represent categorical factors will be clearly defined in the codebook. Units for each continuous variable will be unambiguously indicated for each variable. Each release of the analysis set will be accompanied by the corresponding version of the codebook. Version numbering with dates will be strictly observed.

14.10 Monitoring

We will maintain a record of changes to the REDCap database. Database errors include (a) missing information, (b) erroneous information, and (c) errors arising from difficulties with the electronic forms themselves. Weekly quality assurance reports will summarize the number of each of these. Most importantly, we will closely monitor the time between the study visit date and submission of the electronic forms to REDCap to ensure that this time is less than 3 days. If entry times exceed 5 days, then this will trigger a response, which may include investigation and/or reassignment.

14.11 Data Analysis

Following data checks by the data analyst, the Data Analysis Committee will be responsible for analyzing the data from the REDCap database. It will merge the masked data with the randomization list, perform statistical analyses and prepare reports.

Standard report-generation software included with the R statistical and data analysis package will be used to ensure consistency of the codebook and analysis set at all times.

Data monitoring reports will be prepared based on analysis data sets. These will be prepared using report-generation software. Monitoring reports will include (a) recruitment reports for each center, (b) compliance reports, (c) retention reports, and (d) data quality reports. These will be reviewed by the Coordinating Center on a weekly basis.

14.12 Data Storage and Security

Electronic forms will be completed on an encrypted electronic device, requiring a passcode to unlock the device and additional separate login credentials to access the REDCap forms. Copies of the electronic forms will not be stored on the device itself but rather within the secured REDCap database.

All electronic storage will be subject to standard security procedures in compliance with established enterprise information security standards. Each computer will be hardware-firewalled and will not be accessible outside the Local Area Network. Hard-disk encryption will be used for each machine, and the machine will not be accessible without a network account and password. Only study-specific personnel will have password access to the encrypted Box directory. Accounts will be immediately deactivated for data entry or other personnel who leave the study.

15 Data and Safety Monitoring Committee Charter

This charter is for the Data and Safety Monitoring Committee (DSMC) for the *Azithromycin for COVID-19 Treatment in Outpatients Nationwide (ACTION)* Trial.

The Charter will define the primary responsibilities of the DSMC, its relationship with other trial components, its membership, and the purpose and timing of its meetings. The Charter will also provide the procedures for ensuring confidentiality and communication, statistical monitoring guidelines to be implemented by the DSMC, and an outline of the content of the Open and Closed Reports that will be provided to the DSMC.

The DSMC will be advisory to the trial leadership group, hereafter referred to as the Steering Committee (SC). The SC will be responsible for promptly reviewing the DSMC recommendations and determining, whether to continue or terminate the trial, and to determine whether amendments to the protocol are required. If needed, the DSMC may seek the advice of a content expert outside of the committee.

15.1 DSMC Membership

The DSMC is an independent multidisciplinary group consisting of epidemiologists, biostatisticians, bioethicists, and clinicians that collectively has experience in the management of infectious diseases and in the conduct and monitoring of randomized clinical trials.

The DSMC membership has been restricted to individuals free of apparent conflicts of interest. The source of these conflicts may be financial, scientific, or regulatory. Thus, neither study investigators nor individuals employed by the sponsor, nor individuals who might have regulatory responsibilities for the trial products, are members of the DSMC.

15.2 Conflicts of Interest

The DSMC members will disclose to fellow members any consulting agreements or financial interests they have with the sponsor of the trial, with the contract research organizations (CRO), or with other sponsors having products that are being evaluated or that are competitive with those in the trial. The DSMC will be responsible for deciding whether these consulting agreements or financial interests materially impact their objectivity.

The DSMC members will be responsible for advising fellow members of any changes in any of the membership requirements that occur during the course of the trial. It may be appropriate for DSMC members who develop significant conflicts of interest resign from the DSMC.

DSMC membership is to be for the full duration of the trial. If any members leave the DSMC, the SC, in consultation with the DSMC, will promptly appoint a replacement.

15.3 Timing and Purpose of the DSMC Meetings

Organizational Meeting

The initial meeting of the DSMC will be an Organizational Meeting. This is during the final stages of protocol development and the purpose is to provide advisory review of scientific and ethical issues relating to study design to discuss the standard operating procedures and to discuss the format and content of the Open and Closed Reports that will be used to present trial results.

The Organizational Meeting will be attended by all DSMC members, lead trial investigators, and the trial biostatistician.

Formal Interim Analysis Meetings

One or more 'Formal Interim Analysis' meetings will be held to review data relating to treatment safety and efficacy, and quality of trial conduct.

15.4 Procedures to Ensure Confidentiality and Proper Communication

To enhance the integrity and credibility of the trial, procedures will be implemented to ensure the DSMC has access to all emerging information from the trial regarding comparative results of efficacy and safety, aggregated by treatment arm.

Closed Sessions

Sessions involving only DSMC members and, where appropriate, those unmasked trial investigators (on the Data Coordinating Committee) who generate the Closed Reports (called Closed Sessions) will be held to allow discussion of confidential data from the trial, including information about the relative efficacy and safety of interventions.

At a final Closed Session, the DSMC will develop a consensus on its list of recommendations, including that relating to whether the trial should continue.

Open Session

In order for the DSMC to have access to information provided, by study investigators, or members of regulatory authorities, a joint session between these individuals and DSMC members will be held between the Closed Sessions.

Open and Closed Reports

For each DSMC meeting, Open and Closed Reports will be provided. Open Reports, will include data on recruitment and baseline characteristics, pooled data on eligibility violations, and completeness of follow-up and compliance. The study statistician ([name]) will prepare these Open Reports.

Closed reports, available only to those attending the Closed Sessions of the meeting, will include analyses of primary and secondary efficacy endpoints, including subgroup and adjusted analyses, AEs and symptom severity, and Open Report analyses that are displayed by intervention group. These Closed Reports will be prepared by the study biostatistician.

The Open and Closed Reports should provide information that is accurate, with follow-up that is complete to within two months of the date of the DSMC meeting. The Reports should be provided to DSMC members approximately three days prior to the date of the meeting.

Minutes of the DSMC Meeting

The research team will prepare minutes for the open portion of the meeting, including the DSMC's recommendations.

Recommendations to the Steering Committee (SC)

At each meeting of the DSMC during the trial, the committee will make a recommendation to the Steering Committee to continue or terminate. This recommendation will be based primarily on safety and efficacy considerations and will be guided by statistical monitoring guidelines defined in this Charter.

Recommendations to amend the protocol or conduct of the study made by the DSMC will be considered and accepted or rejected by the SC. The SC will be responsible for deciding whether to continue or to stop the trial based on the DSMC recommendations.

The DSMC will be notified of all changes to the protocol or to study conduct. The DSMC concurrence will be sought on all substantive recommendations or changes to the protocol or study conduct prior to implementation.

The SC may communicate information in the Open Report to the sponsor and may inform them of the DSMC recommended alterations to study conduct or early trial termination in instances in which the SC has reached a final decision agreeing with the recommendation. The SC will maintain confidentiality of all information it receives other than that contained in the Open Reports until after the trial is completed or until a decision for early termination has been made.

15.5 Statistical Monitoring Guidelines

The SC will propose statistical rules for a futility stopping rule (requested by the sponsor) and an efficacy stopping rule at the first DSMC meeting.

APPENDIX

Appendix 1: Original manual of procedures

REVISION HISTORY

4/9/2020: Addition of 21 day follow up timepoint, added additional details to the Study Methods Chapter.

4/10/2020: Addition of Pfizer information to Medication Chapter, addition of Chapter 12 Study Monitoring.

4/19/2020: New eligibility criteria added (QT prolongation + chloroquine over 55).

4/20/2020: Chapter 5 and 6: addition of a sub-study where 100 patients per arm are asked to collect nasal, saliva, and rectal swabs at days 3, 7, 14. Addition of chapter 8: Staff responsibilities.

4/21/2020: Addition of adverse events and SAE information per request of Pfizer.

4/24/2020: Addition of Pfizer SAE reporting requirements.

4/27/2020: Addition of section 3.3 Sub-Studies. Addition of Death as a secondary endpoint. Addition of eligibility criteria (not currently taking nelfinavir or warfarin). Section 5.10 change of patient ID number to REDCap based.

4/28/2020: Addition of figure 1 in 3.3. Change in main study swabs from first 300 participants to all participants will be asked to collect rectal swab at day 3.

5/4/2020: Specification that we will exclude pregnant women. Addition of FDA reporting criteria to SAE section.

5/5/2020. Addition of protocol violation section, drug storage section, concurrent medications section

5/6/2020: Specification of cardiovascular related events for reportable serious adverse events to Pfizer

5/12/2020: Removal of rectal swab in group 1 & group 2 in swab sub-study section.

5/26/2020: Addition of [name] and [name] to the protocol. Addition of color-coded sticker scheme for kits to section 5.10. Addition of lot numbers from drug to 10.4.

6/3/2020: Addition of online social media ad campaign under recruitment.

6/8/2020: Expansion of eligibility criteria “positive test within past 3 days” to “positive test within past 7 days”. Specified that participant can fill out questionnaires via email or over the phone in eligibility criteria.

7/8/2020: Addition of unmasking protocol to 3.6.1.

8/24/2020: Addition of protocol for short form method of consent.

9/23/20: Addition of Rhode Island Open Door Health as recruitment site. Addition of EDDM to recruitment methods. Addition of random drawing lottery.

11/13/20: Addition of WebMD to recruiting methods. Addition of language for obtaining informed consent from computer illiterate participants.

12/7/20: Change primary outcome. Moved hospitalization to secondary outcome.

- The investigators edited the primary outcome to a symptom based outcome. Instead of a hospitalization at Day 14 post enrollment, the primary outcome will be a binary assessment of whether the participant is symptom free at Day 14 (yes or no) post enrollment. This change was made because the trial will not have enough statistical power for the original hospitalization outcome. The event “hospitalization” is much rarer

in the study population than anticipated and enrollment is slower than planned. This change was approved by the trial's Data Safety Monitoring Committee and Institutional Review Board.

12/18/20: Updated objective and sample size.

4/5/21: Addition of section 5.12 Emergency Room Follow-Up.

REFERENCES

## 2. Introduction

### 2.1. Background and rationale

Identification of a safe, effective treatment for individuals with mild or moderate COVID-19 that prevents disease progression and reduces hospitalization would reduce the burden on the health system. High dose hydroxychloroquine is being evaluated for SARS-CoV-2 prevention and COVID-19 disease treatment, but has a high risk of a number of potentially severe adverse events. Recent evidence has indicated that the broad-spectrum macrolide azithromycin may have some activity against coronaviruses. A large community randomized trial in Niger demonstrated reduced viral load among children with commensal coronaviruses (prior to the emergence of SARS-CoV-2) in communities receiving biannual mass azithromycin distribution compared to placebo (submitted). In SARS-CoV-2 patients in France, the addition of azithromycin to a hydroxychloroquine regimen appeared to decrease SARS-CoV-2 positivity by PCR compared to hydroxychloroquine-only and control patients. Azithromycin is generally well-tolerated and may be an attractive option for treating patients with mild disease.

### 2.2. Objectives

1: To determine if a single oral dose of azithromycin is effective for reducing progression to hospitalization in patients with a positive SARS-CoV-2 PCR test with mild or moderate disease.

## 3. Study Methods

### 3.1. Trial design

The trial will be a scalable, telemedicine-based parallel group simple trial to evaluate the efficacy of azithromycin for the prevention of COVID-19 disease progression and hospitalization.

### 3.2. Randomization

Participants will be randomized 2:1 to either receive a dose of oral azithromycin or oral placebo. Patients will be twice as likely to receive azithromycin than placebo. The randomization will not be stratified or blocked in any way. We found that even with permuted block sizes and  $\geq 6$  labels (4 azithromycin, 2 placebo), a 2:1 allocation could lead to unmasking through longer runs of active treatment labels.

### 3.3. Sample size

The trial's revised target enrollment is 455 participants, which will be sufficient to detect an increase in the proportion of patients who are symptom free 50% to 65% (15 percentage point increase) at 14 days from enrollment.

With 455 participants, the trial will have 80% power to detect an increase of 15 percentage points in the percentage of patients who are symptom free at 14-d under the following assumptions:

- 2:1 allocation ratio of azithromycin : placebo
- 50% symptom-free under placebo at the 14-day measurement (binomial outcome)
- 20% loss to follow-up
- 2-sided alpha of 0.05, power = 0.8.

- A single interim analysis with 50% of primary outcomes collected with stopping guideline determined using the Lan-DeMets spending function approach with an O'Brien and Fleming boundary.

The table below shows sample sizes under several effect size scenarios, assuming azithromycin increases the proportion of patients who are symptom free by 0.1 to 0.2 compared to placebo.

Sample size required for a fixed design allowing for 20% loss to follow-up. Calculations assume 2-sided alpha of 0.05 and 80% power.

p placebo	p azithro	RD	N placebo	N azithro	N Total
0.5	0.60	0.10	348	695	1,043
0.5	0.61	0.11	287	573	860
0.5	0.62	0.12	240	479	719
0.5	0.63	0.13	204	407	611
0.5	0.64	0.14	175	349	524
0.5	0.65	0.15	152	303	455
0.5	0.66	0.16	133	265	398
0.5	0.67	0.17	117	233	350
0.5	0.68	0.18	104	207	311
0.5	0.69	0.19	93	185	278
0.5	0.70	0.20	83	165	248

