3.5 Sample Size

The COVID-19 epidemic is changing rapidly over time. We propose a group sequential design with a flexible sample size that is adaptive to changing trial parameters over time with no maximum sample size. These designs are used in outbreak trials due to uncertainty with respect to parameters such as incidence and severity of outcomes. Full details on the sample size are provided in the Statistical Analysis Plan. In brief, the trial will employ a committee that is masked to results by arm that will evaluate the sample size on a weekly basis to evaluate the sample size based on the probability of hospitalization and enrollment.

On December 2, 2020 the DSMC members agreed to revise the sample size and primary outcome of the trial. Our re-estimated sample size of N=455 would allow for detection of a 15% absolute difference in probability of being symptom free at 14 days assuming that 50% in the placebo arm are symptom free (this is based on the current overall percent of participants who are symptom free at 14 days in ACTION). Because ACTION is enrolling more slowly than we had anticipated and we are planning a smaller sample size and we are also planning a single interim analysis at approximately 50% enrollment (N=230 participants), testing for efficacy at $p=0.001$, and then assess the final outcome at $p=0.049$.

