## One-sided group sequential design with
## 80 % power and 2.5 % Type I Error.
##

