### 6.2. Analysis methods

#### Primary Outcome:

The primary analysis will estimate the risk difference (RD) comparing the proportion of patients who are symptom-free at 14 days in the azithromycin versus placebo arms. We will compute *P*-

values for differences between arms using a permutation test with the prevalence difference between arms as the test statistic and 10,000 iterations. We will additionally estimate and report the prevalence ratio.

Determination of statistical significance for the primary and secondary analyses will follow the final alpha-spending function determined by the interim analyses (see section 3.5).

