- Seven interim analyses at 30%, 40%, ..., 90% of outcomes collected with stopping guideline determined using the Lan-DeMets spending function approach with an O'Brien and Fleming boundary.

The table below shows sample sizes under five effect size scenarios, assuming azithromycin reduces hospitalization or death by between 1% (RR = 0.9) and 5% (RR = 0.5) compared to placebo.

Sample size required for a fixed design allowing for 15% loss to follow-up. Calculations assume 2-sided alpha of 0.05 and 80% power.

p placebo	p azithro	RD (ITT)*	RR (ITT)*	N placebo	N azithro	N Total
0.099	0.09	-0.009	0.909	14,221	28,441	42,662
0.098	0.08	-0.018	0.816	3,346	6,691	10,037
0.097	0.07	-0.027	0.722	1,392	2,784	4,176
0.096	0.06	-0.036	0.625	729	1,457	2,186
0.095	0.05	-0.045	0.526	431	861	1,292

\* Risk difference (RD) and risk ratio (RR) under an ITT analysis assuming that 10% of all participants seek azithromycin from sources outside of the trial. This noncompliance has been included in the assumptions of the probability of hospitalization under placebo, from a base of 0.1.

Note, these estimates do not account for interim analyses in a group-sequential analysis. Sequential randomized controlled trials have been demonstrated to result in overall better patient outcomes during fast-moving epidemics because they reach answers for efficacy more quickly than a trial without interim analyses [3].

Using the scenario of a 4% reduction in hospitalization due to placebo, we estimated the maximum sample size under a group-sequential design. Under the assumptions in Section 3.5

(below), the maximum sample size would be **2,268**, a 3.5% increase over a design with no interim monitoring due to alpha spending at 7 interim analyses.

We note that ACTION is designed as a scalable trial. If pre-specified, interim sample size calculations or external factors suggest that increasing the sample size would be desirable, then the masked investigator group that evaluates interim sample size assessments at 30% and 50% enrollment will make a recommendation to the trial's Data and Safety Monitoring Committee, which together will decide if such expansion is desirable. An expansion to approximately 10,000 participants would allow for the detection of smaller but still clinically relevant effects (RR=0.8) given the severity of hospitalization or death.

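### At the SAP's own 20% loss to follow-up, 455 participants give about 78.5% power, not 80%: the sample size table multiplies by 1.2 where it should divide by 0.8

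*SAP*

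**What the plan says.** SAP 3.3 sets the revised target at 455 and states: "With 455 participants, the trial will have 80% power to detect an increase of 15 percentage points". The listed assumptions are 2:1 allocation, 50% symptom free on placebo (so 65% on azithromycin), 20% loss to follow-up, two-sided alpha 0.05, power 0.80, and one interim analysis at half the outcomes with a Lan-DeMets O'Brien-Fleming boundary.

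The table beneath is labelled "Sample size required for a fixed design allowing for 20% loss to follow-up". Its row for 50% versus 65% gives 152 + 303 = 455. The step from evaluable to enrolled participants is not shown; the SAP refers to a companion notebook that is not among the documents.

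SAP 3.5 prints a group-sequential design with "80 % power and 2.5 % Type I Error" and a final N of 456. It states no loss rate of its own. Protocol 3.5 gives N=455 for a 15-point difference but states neither a power nor a loss rate.

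**The concern.** If a fraction L of enrolled participants is lost, N enrolled yields N(1 - L) outcomes, so the evaluable number must be divided by 1 - L. Multiplying by 1 + L gives too few: 20% extra enrollment covers a loss of only 1 - 1/1.2 = 16.7%. SAP 3.3 is the only place that pairs a power with a loss rate. If the pair does not agree, the trial's main design claim is wrong, and a report that copies it will repeat the error.

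**Working it through.** **Inputs (SAP 3.3).** p0 = 0.50, p1 = 0.65, allocation k = 2, two-sided alpha 0.05 (z = 1.960), power 0.80 (z = 0.8416), loss 20%.

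**Evaluable number.** The pooled proportion is (0.50 + 2 × 0.65)/3 = 0.60. The placebo-arm size is

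n0 = [1.960 × √(0.60 × 0.40 × 1.5) + 0.8416 × √(0.50 × 0.50 + 0.65 × 0.35/2)]² / 0.15²

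= [1.960 × 0.6000 + 0.8416 × 0.6031]² / 0.0225 = 1.6836² / 0.0225 = 125.97.

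The total is 3 × 125.97 = 377.92, or 126 + 252 = 378 in whole participants.

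**Reproducing the SAP's figure.**

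| Allowance | Placebo | Azithromycin | Total |
|---|---|---|---|
| × 1.2, rounded up per arm | 151.17 → 152 | 302.34 → 303 | 455 |
| ÷ 0.8, rounded up per arm | 157.47 → 158 | 314.93 → 315 | 473 |

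The × 1.2 rule matches both arm sizes and the total in all 11 rows of the table; ÷ 0.8 matches none. For the 0.65 row, ÷ 0.8 with other variants gives 476 (unpooled variance), 478 (simple-average pooled), 476 (arcsine) and 509 (continuity corrected), never 455.

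Two further checks point the same way:

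- The superseded version 5 table in the SAP appendix, used here only as evidence of the formula, is labelled "Sample size required for a fixed design allowing for 15% loss to follow-up". Multiplying by 1.15 reproduces all 5 rows (for example 729 + 1,457 = 2,186). Dividing by 0.85 reproduces none (745 + 1,490 for the same row).
- The two-look boundary recomputes to Z = 2.963 and 1.969, matching the 2.96 and 1.97 in SAP 3.5, with an inflation factor of 1.0037. Then 377.92 × 1.2 × 1.0037 = 455.2. At that N the standardized effect is 0.1316, as printed. With ÷ 0.8, N would be 474.2 and the effect about 0.129.

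**Power the design delivers at 20% loss.** 455 × 0.80 = 364 outcomes, or 121.33 in the placebo arm. The normal deviate is (0.15 × √121.33 − 1.960 × 0.6000)/0.6031 = (1.6523 − 1.1760)/0.6031 = 0.790. Power is therefore 78.5% for the fixed design, and 78.4% with the interim look. Taking 20% off each of the 11 table rows gives 78.4% to 78.7%.

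**Loss that 455 can absorb at 80% power.** 1 − 377.92/455 = 16.9% for the fixed design. With the interim look it is 1 − (377.92 × 1.0037)/455 = 16.6%.

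**Enrollment for 80% power at 20% loss.** 473 for the fixed design (18 more, 4%), or about 474 to 475 with the interim look.

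**Separate notes, not caused by the loss allowance.**

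- SAP 6.2 tests the primary outcome "using a permutation test with the prevalence difference between arms as the test statistic and 10,000 iterations". It does not say how the two-sided P-value is formed. Exact fixed-margin calculations, single stage at P ≤ 0.049, give these powers:

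| Outcomes (placebo/azithromycin) | On the absolute difference | Doubling the one-sided P |
|---|---|---|
| 121/243 | 76.3% | 74.4% |
| 122/242 | 77.1% | 74.9% |
| 126/252 | 77.7% | 76.2% |

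- Protocol 3.5 says of the 50% that "this is based on the current overall percent of participants who are symptom free at 14 days in ACTION". If 50% is the rate across both arms and the 15-point effect is real, then (p0 + 2(p0 + 0.15))/3 = 0.50 gives p0 = 0.40. For 40% versus 55%, power at 364 outcomes is 77.3% (77.2% with the interim look).

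**The case against.** The strongest counter-argument is size. The loss of power is 1.5 points. Put another way, 364 outcomes still give 80% power for 50% versus 65.3%, so the detectable difference moves from 15.0 to about 15.3 points. Uncertainty about the placebo rate matters at least as much. The table's Ns are usable if the loss is relabelled at about 17%. All of this stands, and it is why no change to enrollment or analysis is proposed.

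The multiplication by 1.2 is an inference, because the notebook is not available. That is true, but an exact match on 22 arm sizes, with the same pattern in the earlier table, leaves little room for another explanation. The 78.5% follows from 455, 20% and the stated rates alone.

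Recomputing the table puts 473 in the 0.65 row beside a target of 455. The two are compatible once the text says what power 455 provides at 20% loss.

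The group-sequential output in SAP 3.5 names no loss rate, so its 80% fails only when the 20% from SAP 3.3 is carried over. That is correct; a cross-reference is enough there.

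Sizing by a normal approximation is ordinary practice, and the permutation-test and 40% versus 55% points are separate matters. They are kept apart for that reason, and the conclusion rests on neither.

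**Conclusion.** The concern holds. Under the SAP's own assumptions, 455 participants give about 78.5% power (78.4% with the interim look), against the 80% stated, and every row of the table falls short by a similar amount. The interim look is not the cause: it adds only 0.4% to N. The power figures use the pooled normal approximation, which reproduces the SAP's table exactly. The documents report no observed loss rate, so whether the trial had 80% power in practice depends on whether actual loss stayed below about 17%. The error is small and confined to the design statement.

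**What to change.** 1. In SAP 3.3 keep N=455 and restate the claim in one of two ways: with 20% loss (364 outcomes) power is about 78%, or 80% power holds for loss up to about 17%.
2. Recompute the table as n/(1 − 0.20), rounded up per arm. The totals for azithromycin rates 0.60 to 0.70 become 1,086, 896, 749, 636, 546, 473, 414, 365, 324, 288 and 258.
3. Add the same note under the group-sequential output in SAP 3.5. Protocol 3.5 states no power or loss rate and needs no correction.
4. Separately, label these powers as normal-approximation figures, since the planned permutation test is somewhat more conservative, and define its two-sided P-value. A sensitivity row for 40% versus 55% is optional.

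The cost is one sentence, one table and one note, plus a slightly less favourable stated power. There is no added enrollment and no change to the analysis.
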